The Informed Consent process may be completed in-person or through an IRB/EC approved remote method. After completing the Informed Consent process, candidates who agree to enter the study must sign and date the IRB/EC approved ICF. The ICF must be signed and dated prior to onboarding. Study data will not be collected until the ICF has been signed and dated. If the candidate does not wish to participate (does not sign and date the ICF), data for that candidate will not be collected for this study.

A copy of the signed and dated ICF must be provided to the study subject. The original signed and dated ICF is to be filed in the subject's medical record, study subject binder, or regulatory binder.

D. Subject Enrollment

Once the ICF has been signed and dated by the subject, the subject will be considered enrolled in the study. A unique subject identification number (Subject ID) will be assigned to each participating subject.

This unique Subject ID number will be used throughout the study for identification. The subject will be considered an active study subject after receiving training in the appropriate use, participation and functionality of the mymobility platform and Apple Watch. In the event that the subject does not undergo knee or hip arthroplasty as outlined in the inclusion criteria, the subject will be considered a screen failure and a **Study Completion Form** will be used to document the subject's exit from the study.

E. Baseline/Preoperative Assessment

The following baseline/pre-operative data will be collected at the time of enrollment:

1. Inclusion/Exclusion Criteria
 - a. Randomization (RCT cohort only, recorded in EDC)
2. Demographics & History Form
3. Pre-op Physical Exam
 - a. Knee/Hip specific assessments including ROM

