| Study Objectives/Endpoints (RCT) | 
To determine if mobile application-guided education and exercise paired with accurate and sensitive activity monitoring, captured from consumer wearables for the entire episode of care can provide a viable (and potentially improved) alternative to current standard of care (SOC) for hip and knee arthroplasty.
 
Primary Endpoint: Non-inferior results between the current SOC and the mymobility platform for all-cause 30-day readmission rates.
 
Secondary endpoints include KOOS, JR. (Knee); HOOS, JR. (Hip), manipulation under anesthesia (knee), single leg stance test, timed up and go (TUG), satisfaction for those subjects who complete the mymobility program compared to those who complete traditional, standard of care education and rehabilitation.
 
Economic Analysis: Determine if subjects who complete the mymobility program incur less cost and fewer resources than subjects receiving traditional SOC. Potential data collection points include: number of PT visits, discharge disposition, ER visits, readmissions, reoperations, unscheduled surgeon visits, and time processing paperwork and approvals for the entire episode of care (30 days prior to surgery through 90 days post-op).
 |
| Indications/Target population | Inpatient and outpatient (including ASC) subjects indicated for unilateral, primary total or partial knee arthroplasty or total hip arthroplasty who meet the inclusion/exclusion criteria for study participation. |
| Inclusion/Exclusion criteria | 
Inclusion Criteria
 
 • Subject must be 18 years of age or older. • Subject qualifies for a primary, unilateral total or partial knee arthroplasty, based on a physical exam |

| | |

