Eligible candidates who express interest in study participation will be offered Informed Consent. All potential study subjects will be required to participate in the Informed Consent process and will not be considered enrolled in the study until the candidate has signed and dated the IRB/EC approved subject Informed Consent Form (ICF). Study data cannot be collected until the candidate has completed the informed consent process and signed and dated the IRB/EC approved ICF.

All study subjects will undergo preoperative and postoperative clinical evaluations as part of the standard of care at each institution. Post-operative clinical evaluations will be conducted after surgery (30 and 90 days). A virtual visit, utilizing the mymobility App or EDC system, will occur at 180 and 365 days post-op.

The target population is patients who have made the decision to undergo a total hip, total knee, or partial knee replacement. The target population is further defined in the inclusion/exclusion criteria in **Section VIII**.

RCT: Primary Endpoint

1. Demonstrate non-inferiority of the study group in the number of readmissions through 30 days post-op.

RCT: Secondary Endpoints

1. Non-inferiority of the mymobility cohort for PROMs (HOOS, JR., KOOS, JR.) and EQ-5D-5L.
2. Manipulation Rates (knee), Timed Up and Go (TUG) and single leg stance test (SLS).
3. Satisfaction/Engagement: Assess differences between the study groups in subject satisfaction from Custom Satisfaction Survey(s).
4. Resource Utilization: Assess differences in resource-utilization in the study group for the entire episode of care (90 days postoperative). Potential data collection points include number of PT visits, discharge disposition, emergency room visits, readmissions, reoperations, unscheduled surgeon visits, and reduction in time processing paperwork and approvals from PT.

VIII. Study Population

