- Research coordinators should contact mymobility Technical Support to document any problems subjects are having with mymobility usage.
 - Research coordinators can also review the clinical dashboard to assess if study subjects are using the mymobility care platform and, together with the clinical team, will contact study subjects at clinically appropriate timelines who do not appear to be adhering to their daily, assigned regimen.

3. Discharge Disposition and Prescribed Physical Therapy

- i. It is intended that after surgery, study subjects will utilize the monitored home exercises within the mymobility platform to reduce the need for in person outpatient physical therapy. Physical therapy prescribed at time of discharge will be documented on the **Procedure & Perioperative Information Form** with the clinical reasoning.
- ii. All subjects receiving physical therapy will remain in the analysis of the study group.
- iii. If subjects are discharged to a postoperative nursing facility, they will continue using the mymobility with Apple Watch application(s) and continue to track all prescribed mymobility activities and passively-collected biometrics as described above.

4. Week 1 after surgery

- i. Study subjects will begin their assigned, mymobility guided, home-based care pathway immediately upon discharge (these subjects will also have had the extensive preoperative teaching pathway from mymobility to prep them for their independent post-op therapeutic exercises).
- ii. Study subjects are recommended not to have any scheduled home PT visits or home health visits, however, should subjects require these services they may be prescribed physical therapy and remain in the study.
- iii. For those study subjects not receiving physical therapy, the surgeon's office may contact patients during the first post-op week to ensure they are comfortably using the mymobility App with Apple Watch platform in the place of standard physical therapy.

5. Postoperative Week 2 through Day 90

- i. Study subjects will be encouraged not to participate in any formal outpatient post-operative physical therapy, however the surgeon has the opportunity to prescribe physical therapy at any time and for any duration during the course of recovery.

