Serious Adverse Events and Serious Adverse Device Effects will be reported to the Sponsor as soon as possible. The incidence will be documented on the Adverse Event Report form over the whole time of the investigation including information on the date of onset, treatment and resolution, as well as assessment of both the seriousness and the relationship to the study device based on the evaluation of the investigator. The outcome of such complications will be documented and any changes in outcome will be updated during the course of the study. In case of early termination of the study, further follow-up of the study subject shall proceed according to the hospital's standard procedure.

Device Deficiencies (including the device, mymobility App, and Apple Watch) that did not lead to an adverse event but could have led to a medical occurrence if suitable actions had not been taken, if intervention had not been made, or if circumstances had been less fortunate shall be reported to the Sponsor as soon as possible.

The Investigator is responsible for reporting all SAEs, SADEs and Device Deficiencies that could have led to a SADE to the Ethics Committee or Institutional Review Board if required by national regulations or by the EC/IRB.

The Sponsor is responsible for determining the final classification of adverse events.

3. Revision

In the event that removal of one or more of the implanted devices used in the joint arthroplasty procedure is necessary, the Investigator will determine the best treatment and/or revision method for the subject.

Once the revision surgery has been completed, the Investigator or qualified Designee must complete an **Adverse Event Form**. Subjects who have tibial articulating surface exchanges may remain enrolled in the study. All other revisions will result in the subject being terminated from the study and a **Study Completion Form** must be completed.

4. Investigator Withdrawal

The Investigator can choose to withdraw a subject from the study if it is deemed to be in the subject's best interest or the subject does not consent to continue in the study after being informed of changes in the research that might affect them. The reason for the Investigator's withdrawal of the subject must be documented on the **Study Completion Form**.

5. Subject Withdrawal

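### The synopsis compares RCT arms among subjects who complete a programme, with the cost filter on the app arm only; Section VII compares by study group, and no as-randomised analysis set is named

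*Combined protocol and SAP*

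**What the plan says.** Four places bear on who is compared with whom in the RCT.

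- **Study Synopsis, Study Objectives/Endpoints (RCT).** The secondary endpoints (KOOS, JR., HOOS, JR., manipulation, single leg stance, TUG, satisfaction) end with "satisfaction for those subjects who complete the mymobility program compared to those who complete traditional, standard of care education and rehabilitation". Both arms carry the condition.
- **Same cell, Economic Analysis.** "Determine if subjects who complete the mymobility program incur less cost and fewer resources than subjects receiving traditional SOC". Only the app side carries the condition.
- **Section VII, RCT: Secondary Endpoints.** No completion condition appears. The patient-reported outcome item reads "Non-inferiority of the mymobility cohort for PROMs (HOOS, JR., KOOS, JR.) and EQ-5D-5L", the resource item reads "Assess differences in resource-utilization in the study group for the entire episode of care (90 days postoperative", and satisfaction is compared between the study groups.
- **Section XI.A.3.** "All subjects receiving physical therapy will remain in the analysis of the study group".

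Completion is defined nowhere. Section VIII describes the population for the primary analysis by procedure and eligibility, not by allocation. Section XVI names no analysis set and no missing-data method for the RCT comparisons.

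Randomisation takes place at the pre-operative visit after consent (Section XI.B.2), and the pre-operative interval runs up to 180 days before surgery. Under Section X.D, when the arthroplasty does not take place, "the subject will be considered a screen failure" and leaves the study.

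**The concern.** Whether someone completes an exercise and education programme depends partly on how recovery goes, and recovery is what the trial measures. Selecting on it after allocation gives up the comparability that randomisation bought. The cost sentence is the more serious of the two, because no filter on the control side could offset the selection.

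The conflict adds a second problem. With one population in the synopsis, another in Section VII and no definition in Section XVI, an analyst could settle the population after seeing the data. The claims at stake are lower cost, less PT, and similar or better function and satisfaction.

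**Working it through.** **1. The plan's own figure.** The only computed RCT figure is the 794 in Section XVI.B. Inputs: 5.4% readmission in both arms, margin 4.5 points, 80% power, alpha 0.05. Taking alpha as two-sided:

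n per arm = (1.960 + 0.842)² × 2 × 0.054 × 0.946 / 0.045² ≈ 396.0, rounded up to 397, so 794 in total.

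This matches. Allowing for 20% loss, 794/0.80 = 993, which the plan rounds to 1,000. The wording of the primary endpoint has no completion condition, so nothing below changes these figures. No figure is given for the secondary or economic comparisons.

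**2. Cost wording, app arm filtered only.** Let V be the control mean number of PT visits and f the share of the app arm that does not complete. Assume app completers need no PT and app non-completers use V.

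- As-randomised difference: fV − V = −(1 − f)V
- Difference using app completers only: 0 − V = −V
- Overstatement of the saving: 1/(1 − f) − 1

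| Non-completion f | As-randomised saving | Completer saving | Overstated by |
|---|---|---|---|
| 5% | 0.95 V | V | 5% |
| 10% | 0.90 V | V | 11% |
| 20% | 0.80 V | V | 25% |

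The values of f and the two usage assumptions are mine; the documents give neither. The bias is zero if non-completers use the same resources as completers, and it reverses if they use less.

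**3. Secondary wording, both arms filtered.** Suppose there is no true effect, and non-completers score g SD worse than completers in both arms. Dropping a fraction f raises an arm's mean by f × g, so the bias towards the app is (f_app − f_control) × g. With 400 per arm (1,000 less 20%, halved) and unit SD:

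SE = √[1/(400(1 − f_app)) + 1/(400(1 − f_control))]

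The chance of a nominally significant result favouring the app is P(Z > 1.96 − bias/SE). With g = 0.5 (assumed):

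| App / control non-completion | Bias towards app (SD) | SE | Chance |
|---|---|---|---|
| 20% / 10% | +0.05 | 0.077 | 9.5% |
| 20% / 20% | 0 | 0.079 | 2.5% |
| 10% / 20% | −0.05 | 0.077 | about 0.5% |

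Satisfaction behaves the same way. Assume 85% satisfied overall in each arm and 60% among non-completers. With 80% completion in the app arm and 90% in the control arm, completer satisfaction is (0.85 − 0.20 × 0.60)/0.80 = 91.25% against (0.85 − 0.10 × 0.60)/0.90 = 87.78%. That is a spurious +3.5 points for the app. Equal completion gives 0, and the reverse pattern gives −3.5 points.

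**4. Do the other passages settle the population?** Section VII points to comparison by group but defines no analysis set. Section XI.A.3 covers only subjects who receive PT and is silent on subjects who simply stop using the app. If receiving PT counts as not completing, it contradicts the synopsis outright; if not, the synopsis filter still applies to the rest.

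**The case against.** The strongest reply is that the body of the protocol already points to analysis by group. Section VII carries no completion condition and Section XI.A.3 keeps PT recipients. The protocol also uses *complete* loosely for undergoing the pathway: Section V describes the whole study group that way, and the Study Design row of the synopsis says all subjects will complete their prescribed activities. No rule drops non-completers. The clause might even attach to satisfaction alone. All of this stands as a reason to call it a conflict in the wording rather than a settled completer analysis. It does not remove the conflict, because nothing says which text governs.

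It is also fair that study success rests on 30-day readmission alone, that Section XVI plans descriptive summaries, and that no test is specified for these endpoints. The error chances above therefore describe a test a reader might apply, not one the plan sets out.

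Some stronger inferences are tempting but not supported:

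- **That every secondary comparison favours the app.** Dropping 20% from the app arm alone with a 0.5 SD gap gives bias 0.10, SE 0.075 and a false-favourable chance of about 27%. But the secondary sentence filters both arms. The 20% crossover figure in Section V also cannot stand in for non-completion, because it concerns patients who move to formal PT, and Section XI.A.3 keeps such subjects in the analysis.
- **That other rules strip the app arm.** Section X.D says "The subject will be considered an active study subject after receiving training in the appropriate use", a step controls do not have, but no passage ties that status to an analysis set or an exit. The screen-failure rule and the revision rule in Section XII.D.3 ("All other revisions will result in the subject being terminated from the study", tibial articulating surface exchanges excepted) apply to both arms, and neither deletes data already collected.

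**Conclusion.** The point holds as an internal conflict with a real risk of bias. Two synopsis sentences condition RCT comparisons on an undefined event after randomisation, Section VII and Section XI.A.3 point the other way, and no analysis set by assigned arm is named.

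For cost, the bias favours the app on the one condition that its non-completers use more resources than its completers. The illustrative overstatement of 5% to 25% rests on assumed non-completion of 5% to 20% and on the two PT-use assumptions. For the secondary endpoints neither direction nor size can be fixed from the documents: the bias is zero with equal non-completion and equal gaps, and may favour either arm otherwise.

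A reader might infer that the main non-inferiority result is compromised. The documents do not support that: the readmission endpoint carries no completion condition and its sample size reproduces. Whether to go on following subjects after a revision is a separate design preference, not part of this point.

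**What to change.** Replace the two completer sentences in the synopsis so that they agree with Section VII and Section XI.A.3, and repeat the definition in Section XVI:

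- Every RCT secondary and economic endpoint is compared by assigned arm in all randomised subjects who had the index surgery, whatever their training, app use or PT.
- Define completion for both arms, and show completer results only in a table labelled as supportive.
- Report randomised subjects who were not operated on, by arm, as post-randomisation exclusions rather than screen failures. The proposed set still leaves them out, so readers need the counts to judge balance.

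The cost is protocol and analysis-plan wording plus one extra row in the subject-flow table. There is no new data collection and no change in sample size. The downside for the sponsor is that the app arm's cost results may look slightly less favourable.

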| | 
and medical history.
 
 Investigator plans to treat subject with a commercially-available device, used on-label according to the manufacturer's instructions for use, as part of their clinical care. Subject owns and maintains an iPhone capable of pairing to the Apple Watch, supporting iOS updates and is compatible with the mymobility App. Subject is willing and able to complete the protocol required follow-up. Subject is able to read and understand the language used in the mymobility App for their region. Subject is willing and able to provide written Informed Consent and Authorization by signing and dating the IRB/EC approved Informed Consent Form and Authorization. Where applicable, subject must also be willing to provide authorization for use of protected health information in accordance with local privacy laws. Subject is mobile with no more than a single cane/single crutch assist preoperatively. 
Exclusion Criteria
 
 Subject is a current alcohol or drug abuser. Subject has inflammatory arthropathies which would interfere or compromise the activity profiles within this study. Subject is considered a member of a protected population (e.g., prisoner, mentally incompetent, etc.). Subject is currently participating in any other surgical intervention, physical therapy or pain management study which would compromise the results of this study. Subject requires simultaneous or staged bilateral replacements, staged <90 days apart. Subjects can be enrolled into the study for the second, staged arthroplasty if scheduled >89 days after their first, contralateral replacement. 
Additionally, subjects who complete the entire study (1 year) for one joint may be enrolled for a second joint.
 |

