3. Subject has systemic inflammatory arthropathies which would interfere or compromise the activity profiles within this study.
4. Subject is currently participating in any other surgical intervention, physical therapy or pain management study which would compromise the results of this study.
5. Subject requires simultaneous or staged bilateral replacements, staged <90 days apart. Subjects can be enrolled into the study for the second, staged arthroplasty if scheduled >89 days after their first, contralateral replacement.

Additionally, subjects who complete the entire study (1 year) for one joint may be enrolled for a second joint as a new subject.

IX. Study Device Information

A. mymobility Product Description

[figure not shown]
The mymobility App is a mobile software platform designed to facilitate remote episode of care management and asynchronous communication between the provider care team and their patient via provider-approved care plans and engagement communications. Current care pathways have been developed for: Total Hip Replacement, Total Knee Replacement and Partial Knee Replacement. Designed for the orthopedic population, mymobility also integrates wearable data from the Apple Watch into provider dashboards, providing enhanced understanding and monitoring of patients throughout the episode of care. This study will utilize version 1.01 of the mymobility App and all future versions as they are released. Version dates will be captured for the purpose of analysis.

Subjects will be provided an Apple Watch to pair with their iPhone for use in the study. If subjects already own a Series 3 or newer Apple Watch, they will be able to use their watch for the study purposes. Details of watch use and data safety are detailed in **Sections XI** and **XII**.

B. mymobility App Overview

1. Patient To Do List

The login screen shows “To Do List”, which identifies assigned activities to be completed during the patient’s episode of care. Examples include: an education ePub (Preparing the Operative Site), a Patient Reported Outcomes Measure (KOOS, JR.), and an exercise routine (Week 1 Routine). Once the patient completes an activity, a check mark will appear next to the item signifying completion.

[figure not shown]
2. Patient Dashboard

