- ii. Around the time of the 30-day and the 90-day time points, subjects will be asked to complete a PROM survey that they will receive through the mymobility App. In addition, an EQ-5D-5L and general satisfaction(s) question will be sent via email through the EDC system.
- iii. Post-operative clinical evaluations will be conducted after surgery (30 and 90 days).

6. Postoperative Day 91 to 365

- i. Subjects will continue wearing their Apple Watch and will keep the mymobility App active. They will continue to receive messages and recovery tips for 365 days following their surgery.
- ii. 180 days after surgery, subjects will be asked to complete a PROM survey that they will receive through the mymobility App. In addition, an EQ-5D-5L questionnaire will be sent to them via email through the EDC system.
- iii. 365 days after surgery, subjects will be asked to complete a final PROM survey that they will receive through the mymobility App. In addition, an EQ-5D-5L questionnaire will be sent to them via email through the EDC system.

7. End of Study

- i. Subject participation will conclude after the final (365 day) PROM survey/satisfaction questionnaires are completed.
- ii. Subjects may uninstall the mymobility App and/or Apple Health and Fitness Recorder from their iPhone.

B. Additional Cohort-Specific Procedures

1. Pilot & Time Study Cohort (N = up to 300, up to 6 centers)

This is an office workflow-focused cohort that will also evaluate study and product onboarding requirements (time and staff), time requirements for instrumentation of the mymobility App and Apple Watch, study execution requirements (time and staff), verifying enrollment assumptions and customized survey content, and time required to attain subject understanding of how to use Apple Watch features (steps, stand hours, active calories, exercise minutes, heart rate - resting, walking, variability, flights climbed)

- i. All pilot study subjects will undergo all study procedures outlined in listed in **Section XI**.
- ii. Additional time and resource data utilization regarding the instrumentation, onboarding and monitoring of subjects with the mymobility platform will be captured.

2. Randomized Controlled Trial (RCT) Cohort (N = 1,000)

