For sites participating in both the Pilot and RCT cohorts, enrollment in the RCT cohort will begin once enrollment is complete at the site for the pilot cohort. Randomization will occur during the pre-operative visit after subjects have signed the ICF for participation in the study. A standard, stratified 1:1 randomization of total hips, total knees, and partial knees will be used to assign subjects to either the mymobility/Apple Watch study group or the standard of care control group. Stratification will ensure that within hips and knees, each procedure type will have a balanced allocation of control

and study patients.

a. Study Group (N=500)

Once randomization is completed, all subjects who were randomized to the mymobility group (mymobility/Apple Watch platform) will undergo all routine study procedures outlined in **Section XI**. In addition, each subject will:

- i. At the preoperative, 30 day and 90 day visits, subjects will undergo a physical exam.
- ii. At the 30 day and 90 day visits, subjects will undergo a Timed Up and Go (TUG) assessment and Single Leg Stance (SLS) assessment. A description of each assessment is listed below:
 - a. TUG assessment: the subject will be asked to rise from a sitting position, walk 3 meters as quickly as they feel safe and comfortable, turn around and walk back to take a seat in the chair. They will be timed from initiation of standing to a return to the sitting position. The subject will get one practice trial prior to scoring the assessment.
 - b. SLS assessment: Three, one-minute maximum, timed observations will be obtained. The average of the three timed observations will be calculated at the time of data analysis.

b. Control Group (N=500)

Subjects randomized to the control group will undergo traditional, standard of care procedures at their institution without the use of the mymobility platform

- i. Control subjects will receive the standard of care (SOC) at the institution, including postoperative PT, and go through normal preoperative standard of care including joint camp classes, preoperative medical clearance, and traditional preoperative education.
- ii. Control subjects will not be provided with the Apple Watch or mymobility App.
- iii. Control subjects will go through each institution's standard of care (SOC) perioperative management pathway.

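### Nothing in the eligibility rules keeps former mymobility users out of the RCT, so a returning participant can be randomised to control; the effect is probably small and the repair is cheap

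*Combined protocol and SAP*

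**What the plan says.** Section VIII.B, after exclusion criterion 5, states that "subjects who complete the entire study (1 year) for one joint may be enrolled for a second joint as a new subject". The synopsis (Section III) gives the same permission, "subjects who complete the entire study (1 year) for one joint may be enrolled for a second joint", without saying that the person counts as new. Neither place limits the permission to one cohort.

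Criterion 5 itself adds: "Subjects can be enrolled into the study for the second, staged arthroplasty if scheduled >89 days after their first, contralateral replacement".

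The nearest exclusion is criterion 4, "Subject is currently participating in any other surgical intervention, physical therapy or pain management study". It concerns current participation in another study, not earlier participation in this one. Sections VII, VIII and X.B ask sites to offer the study to every eligible patient.

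On allocation, Section XI.B.2 says that "A standard, stratified 1:1 randomization of total hips, total knees, and partial knees will be used". Prior participation is not a stratum. Section XI.B.2.b describes control as the institution's usual pathway with no use of the platform, and adds: "Control subjects will not be provided with the Apple Watch or mymobility App". For people finishing a first entry on the app, Section XI.A.7 says: "Subjects may uninstall the mymobility App and/or Apple Health and Fitness Recorder from their iPhone".

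Section X.D says: "A unique subject identification number (Subject ID) will be assigned to each participating subject". It describes no link between two entries by one person. Section XVI names no unit of analysis and gives no rule for repeat entrants.

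**The concern.** The RCT is a non-inferiority comparison of an app-guided pathway with care that does not use the app. Followed as written, the rules allow a control arm that includes people already taught by the app. Not supplying the app a second time does not take away what they learned: Section XI.A.4 relies on the app's preoperative teaching to prepare patients for exercising on their own.

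In a superiority trial such dilution would work against the sponsor's hypothesis. Here it works for it. If the app pathway were truly worse, controls who behave partly like app patients would shrink the observed difference and make non-inferiority easier to declare. Section XVI.C makes non-inferiority on readmission the sole condition for study success.

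**Working it through.** **Is the route open?** A returning completer meets no exclusion, and sites are told to offer entry. The timing allows it: recruitment is about 24 months (synopsis), while a subject's follow-up is about one year. At sites doing both, the pilot cohort, all app users, enrols before the RCT (Section XI.B.2). App-arm completers of the RCT could also return.

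**The plan's own figure.** Inputs from Section XVI.B: 5.4% readmission in both arms, margin 4.5 points, 80% power, alpha 0.05.

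n per arm = 2 × 0.054 × 0.946 × (1.960 + 0.842)² / 0.045² = 396.002, rounded up to 397, so 794 in total. This matches if 0.05 is two-sided (0.025 one-sided). One-sided 0.05 gives 312 per arm, 624 in total, which does not match. With 20% loss, 794 / 0.80 = 993, consistent with 1,000.

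**Former app users in control.** The documents give no re-entry rate, so the share c is an assumption, shown as a range. Assume also full carry-over (a former user in control has the app arm's readmission risk) and a true difference at the margin, 5.4% against 9.9%.

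- Control rate: p(c) = 0.054 + c × 0.045
- Expected difference: D(c) = 0.099 − p(c)
- SE = √{[p(c)(1 − p(c)) + 0.099 × 0.901] / n}
- One-sided type I error = Φ[(0.045 − D(c)) / SE − 1.960]

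For c = 5% and n = 397: p = 0.05625, D = 0.04275, SE = 0.01893. Then 0.00225 / 0.01893 = 0.119, and Φ(0.119 − 1.960) = 0.033.

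| Share c | Controls out of 500 | Expected difference (points) | Type I error, 397 per arm | Type I error, 500 per arm |
|---|---|---|---|---|
| 0% | 0 | 4.500 | 2.5% | 2.5% |
| 1% | 5 | 4.455 | 2.6% | 2.7% |
| 2% | 10 | 4.410 | 2.8% | 2.8% |
| 5% | 25 | 4.275 | 3.3% | 3.4% |
| 10% | 50 | 4.050 | 4.2% | 4.5% |

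**Two records from one person.** Let s be the share of records that come from double entrants and ρ the within-person correlation, both assumed. The variance factor is 1 + sρ if both entries fall in the same arm and 1 − sρ if they fall in opposite arms. For s = 2–10% and ρ = 0.1–0.5, same-arm factors run from 1.002 to 1.05 (equivalent total 796 to 834, power 80.0% to 78.2%), and opposite-arm factors from 0.998 to 0.95. With independent re-randomisation the two roughly cancel: a simulation at s = 10%, ρ = 0.3 gave a variance ratio of 0.99.

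**The case against.** The strongest case against is that the control arm is defined by use as well as supply. Care plans in the app are provider-approved and its tasks are assigned (Section IX), so nothing shows that an app left on the phone would deliver a new pathway to a control. A kept watch adds little, since some patients own one anyway. That stands. What remains is memory of content taught about a year or more before, and its effect on all-cause 30-day readmission is an assumption.

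The shares may also be generous. Under 1:1 allocation, 25 to 50 former users in control imply about 50 to 100 randomised. The pilot holds at most 300, so on its own it would have to supply 50/300 = 17% to 100/300 = 33% of its members. Other app users could add to the pool, but the documents do not show that Cohort III completers would feed an RCT still recruiting. This also stands.

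Three stronger readings are tempting but not supported.

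- A reader might infer that the >89-day sentence lets an RCT control re-enrol and receive the app during the remaining control follow-up, in conflict with the one-year condition. It reads more naturally as covering a first joint replaced outside the study. The document history points the same way: the staged-joint rule was relaxed in version 2.0 and the completer permission was added separately in version 3.0, which would have been needless if re-entry at 90 days were already allowed. This is an ambiguity, and it could not affect the 30-day endpoint of the first entry.
- A reader might infer that duplicated people inflate predictive performance in Cohort III. That presupposes a data split or cross-validation, and Section XVI.C describes neither.
- A reader might infer that returning completers are a selected low-risk group and so bias the trial. Selection before randomisation does not bias the comparison between arms, and some revised patients (tibial articulating surface exchange) may remain enrolled.

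**Conclusion.** The point holds as a gap in what the rules permit, not as something shown to occur. A former app user can be randomised to control, and no criterion, stratum or analysis rule deals with it.

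The size is probably small. The tabulated figures are closer to a ceiling than a forecast: full carry-over gives a former user in control the app arm's whole excess risk, although that person still receives standard care including physical therapy. At a 1–2% share the change in type I error is negligible. At 5–10% it is modest and anti-conservative. Satisfaction and patient-reported outcomes may be more exposed than readmission, but the documents do not allow that to be sized.

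The sample size of 794 is not in error on this account, and double counting is a gap in defining the analysis unit rather than a threat to the primary test. The case for acting rests on how little the repair costs.

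**What to change.** 1. Add an RCT-only exclusion for any previous enrolment in this study or previous use of mymobility. Eligible second-joint patients enter Cohort III instead, without randomisation.
2. Link the Subject IDs of one person. For anyone who has already re-entered, use only first entries without prior app exposure in the RCT analysis, or do so as a sensitivity analysis if enrolment has closed. If Cohort III models are split or cross-validated, keep all of a person's records on the same side.
3. Clarify that the >89-day sentence in criterion 5 does not permit a second enrolment while the first is still in follow-up, and align the re-entry wording in the synopsis with Section VIII.B.

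The cost is one exclusion line, one clarified sentence and one linking field. A few second-joint patients move from the RCT to Cohort III, where they still count towards the 10,000, so RCT recruitment is very slightly slower. The required sample size does not change.
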